Conventional CT and MRI. This guideline has defined measurability of lesions on CT scan based on the assumption that CT thickness is 5mm or less. If CT scans have slice thickness greater than 5 mm, the minimum size of a measurable lesion should be twice the slice thickness. MRI is also acceptable in certain situations (e.g. for body scans).

Use of MRI remains a complex issue. MRI has excellent contrast, spatial, and temporal

resolution; however, there are many image acquisition variables involved in MRI, which greatly impact image quality, lesion conspicuity, and measurement. Furthermore, the availability of MRI is variable globally. As with CT, if an MRI is performed, the technical specifications of the scanning sequences used should be optimized for the evaluation of the type and site of disease. Furthermore, as with CT, the modality used at follow-up should be the same as was used at baseline and the lesions should be measured/assessed on the same pulse sequence. It is beyond the scope of the RECIST guidelines to prescribe specific MRI pulse sequence parameters for all scanners, body parts, and diseases. Ideally, the same type of scanner should be used and the image acquisition protocol should be followed as closely as possible to prior scans. Body scans should be performed with breath-hold scanning techniques, if possible.

FDG-PET. While FDG-PET response assessments need additional study, it is sometimes reasonable to incorporate the use of FDG-PET scanning to complement CT scanning in assessment of progression (particularly possible 'new' disease). New lesions on the basis of FDG-PET imaging can be identified according to the following algorithm:

- (a) Negative FDG-PET at baseline, with a positive FDG-PET at follow-up is a sign of PD based on a new lesion.
- (b) No FDG-PET at baseline and a positive FDG-PET at follow-up: If the positive FDG-PET at follow-up corresponds to a new site of disease confirmed by CT, this is PD. If the positive FDG-PET at follow-up is not confirmed as a new site of disease on CT, additional follow-up CT scans are needed to determine if there is truly progression occurring at that site (if so, the date of PD will be the date of the initial abnormal FDG-PET scan). If the positive FDG-PET at follow-up corresponds to a pre-existing site of disease on CT that is not progressing on the basis of the anatomic images, this is not PD.
- (c) FDG-PET may be used to upgrade a response to a CR in a manner similar to a biopsy in cases where a residual radiographic abnormality is thought to represent fibrosis or scarring. The use of FDG-PET in this circumstance should be prospectively described in the protocol and supported by disease-specific medical literature for the indication. However, it must be acknowledged that both approaches may lead to false positive CR due to limitations of FDG-PET and biopsy resolution/sensitivity.

Note: A 'positive' FDG-PET scan lesion means one which is FDG avid with an uptake greater than twice that of the surrounding tissue on the attenuation corrected image.

PET-CT. the low dose or attenuation correction CT portion of a combined PET-CT is not always of optimal diagnostic CT quality for use with RECIST measurements and will not be used on this trial.

Response Criteria

Evaluation of Target Lesions

Complete Response (CR): Disappearance of all target lesions. Any pathological lymph nodes (whether target or non-target) must have reduction in short axis to <10 mm.

Partial Response (PR): At least a 30% decrease in the sum of the diameters of target lesions, taking as reference the baseline sum diameters.

Progressive Disease (PD): At least a 20% increase in the sum of the diameters of target lesions, taking as reference the smallest sum on study (this includes the baseline sum if that is the smallest on study). In addition to the relative increase of 20%, the sum must also demonstrate an absolute increase of at least 5 mm. (Note: the appearance of one or more new lesions is also considered progressions).

Stable Disease (SD): Neither sufficient shrinkage to qualify for PR nor sufficient increase to qualify for PD, taking as reference the smallest sum diameters while on study.

Evaluation of Non-Target Lesions

Complete Response (CR): Disappearance of all non-target lesions and normalization of tumor marker level. All lymph nodes must be non-pathological in size (<10 mm short axis).

Note: If tumor markers are initially above the upper normal limit, they must normalize for a patient to be considered in complete clinical response.

Non-CR/Non-PD: Persistence of one or more non-target lesion(s) and/or maintenance of tumor marker level above the normal limits.

Progressive Disease (PD): Appearance of one or more new lesions and/or *unequivocal progression* of existing non-target lesions. *Unequivocal progression* should not normally trump target lesion status. It must be representative of overall disease status change, not a single lesion increase.

Although a clear progression of “non-target” lesions only is exceptional, the opinion of the treating physician should prevail in such circumstances, and the progression status should be confirmed at a later time by the review panel (or Principal Investigator).

Evaluation of New Lesions

The finding of a new lesion should be unequivocal (i.e. not due to difference in scanning technique, imaging modality, or findings thought to represent something other than tumor (for example, some ‘new’ bone lesions may be simply healing or flare of pre-existing lesions). However, a lesion identified on a follow-up scan in an anatomical location that was not scanned at baseline is considered new and will indicate PD. If a new lesion is equivocal (because of small size etc.), follow-up evaluation will clarify if it truly represents new disease and if PD is confirmed, progression should be declared using the date of the initial scan on which the lesion was discovered.

Evaluation of Best Overall Response

The best overall response is the best response recorded from the start of the treatment until disease progression/recurrence (taking as reference for progressive disease the smallest measurements recorded since the treatment started). The patient's best response assignment will depend on the achievement of both measurement and confirmation criteria.

For Participants with Measurable Disease (*i.e.*, Target Disease)

Target Lesions	Non-Target Lesions	New Lesions	Overall Response	Best Overall Response when Confirmation is Required*
CR	CR	No	CR	≥ 4 wks Confirmation**
CR	Non-CR/Non-PD	No	PR	
CR	Not evaluated	No	PR	
PR	Non-CR/Non-PD/not evaluated	No	PR	≥ 4 wks Confirmation**
SD	Non-CR/Non-PD/not evaluated	No	SD	Documented at least once ≥ 4 wks from baseline**
PD	Any	Yes or No	PD	
Any	PD***	Yes or No	PD	
Any	Any	Yes	PD	no prior SD, PR or CR

* See RECIST 1.1 manuscript for further details on what is evidence of a new lesion.

** Only for non-randomized trials with response as primary endpoint.

*** In exceptional circumstances, unequivocal progression in non-target lesions may be accepted as disease progression.

Note: Participants with a global deterioration of health status requiring discontinuation of treatment without objective evidence of disease progression at that time should be

reported as “*symptomatic deterioration*.” Every effort should be made to document the objective progression even after discontinuation of treatment.

For Participants with Non-Measurable Disease (i.e., Non-Target Disease)

Non-Target Lesions	New Lesions	Overall Response
CR	No	CR
Non-CR/non-PD	No	Non-CR/non-PD*
Not all evaluated	No	not evaluated
Unequivocal PD	Yes or No	PD
Any	Yes	PD

* ‘Non-CR/non-PD’ is preferred over ‘stable disease’ for non-target disease since SD is increasingly used as an endpoint for assessment of efficacy in some trials so to assign this category when no lesions can be measured is not advised

Modified immune-related response criteria (irRC), derived from RECIST 1.1

This irRC classification is based on the recent learning from clinical studies with cancer immunotherapies that even if some new lesions appear at the beginning of a treatment or if the total tumor burden does not increase substantially, tumor regressions or stabilizations might still occur later. The irRC were created using bidimensional measurements (as previously widely used in the World Health Organization criteria). For this trial, the concepts of the irRC are combined with RECIST 1.1 to come up with the modified irRC.

For modified irRC, only target and measurable lesions are taken into account. In contrast to the RECIST 1.1 criteria, the modified irRC criteria (a) require confirmation of both progression and response by imaging at 8 weeks after initial imaging and (b) do not necessarily score the appearance of new lesions as progressive disease if the sum of lesion diameters of target lesions (minimum of 10 mm per lesion, maximum of 5 target lesions, maximum of 2 per organ) and measurable new lesions does not increase by $\geq 20\%$.

The same method of assessment and the same technique should be used to characterize each identified and reported target lesion(s) at baseline, during the trial, and at the end of trial visit. All measurements should be recorded in metric notation. The modified irRC based on RECIST 1.1 are displayed below.

Modified immune-related response criteria are defined as follows:

New measurable lesions: Incorporated into tumor burden.

New non-measurable lesions: Do not define progression but precludes (irCR).

Overall irCR: Complete disappearance of all lesions (whether measurable or not) and no new lesions. All measurable lymph nodes also must have a reduction in short axis to 10 mm.

Overall irPR: Sum of the longest diameters of target and new measurable lesions decreases $\geq 30\%$.

Overall irSD: Sum of the longest diameters of target and new measurable lesions neither irCR, irPR,

(compared to baseline) or irPD (compared to nadir).

Overall irPD: Sum of the longest diameters of target and new measurable lesion increases $\geq 20\%$ (compared to nadir). It is recommended that overall irPD be confirmed by a follow-up CT at least 4-12 from the date first documented.

Overall responses derived from changes in index, non-index, and new lesions are summarized in the table below.

Overall Responses Derived from Changes in Index, Non-Index, and New Lesions

Measurable Response	Non-Measurable Response		Overall Response Using Modified irRC
Index and New, Measurable Lesions	Non-Index Lesions	New, Non-Measurable Lesions	
Decrease 100%	Absent	Absent	irCR ²
Decrease 100%	Stable	Any	irPR ²
Decrease 100%	Unequivocal progression	Any	irPR ²
Decrease $\geq 30\%$	Absent / Stable	Any	irPR ²
Decrease $\geq 30\%$	Unequivocal progression	Any	irPR ²
Decrease $< 30\%$ to increase $< 20\%$	Absent / Stable	Any	irSD
Decrease $< 30\%$ to increase $< 20\%$	Unequivocal progression	Any	irSD
Increase $\geq 20\%$	Any	Any	irPD

¹ Decreases assessed relative to baseline

² Assuming that the response (irCR and irPR) and progression (irPD) are confirmed by a second, consecutive assessment at least 4 weeks apart (normally it should be done 8 weeks apart).

Duration of Response

Duration of overall response: The duration of overall response is measured from the time measurement criteria are met for CR or PR (whichever is first recorded) until the first date that recurrent or progressive disease is objectively documented (taking as reference for progressive disease the smallest measurements recorded since the treatment started, or death due to any cause. Participants without events reported are censored at the last disease evaluation).

Duration of overall complete response: The duration of overall CR is measured from the time measurement criteria are first met for CR until the first date that progressive disease is objectively documented, or death due to any cause. Participants without events reported are censored at the last disease evaluation.

Duration of stable disease: Stable disease is measured from the start of the treatment until the criteria for progression are met, taking as reference the smallest measurements recorded since the treatment started, including the baseline measurements.

Progression-Free Survival

Overall Survival: Overall Survival (OS) is defined as the time from randomization (or registration) to death due to any cause, or censored at date last known alive.

Progression-Free Survival: Progression-Free Survival (PFS) is defined as the time from randomization (or registration) to the earlier of progression or death due to any cause. Participants alive without disease progression are censored at date of last disease evaluation.

Time to Progression: Time to Progression (TTP) is defined as the time from randomization (or registration) to progression, or censored at date of last disease evaluation for those without progression reported.

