Opdivo can cause immune-mediated rash, including Stevens-Johnson syndrome (SJS) and toxic epidermal necrolysis (TEN), some cases with fatal outcome. For symptoms or signs of SJS or TEN, withhold Opdivo and refer the patient for specialized care for assessment and treatment. If SJS or TEN is confirmed, permanently discontinue Opdivo [see Dosage and Administration].

For immune-mediated rash, administer corticosteroids at a dose of 1 to 2 mg/kg/day prednisone equivalents followed by a corticosteroid taper for severe (Grade 3) or life-threatening (Grade 4) rash. Withhold Opdivo for severe (Grade 3) rash and permanently discontinue Opdivo for life-threatening (Grade 4) rash.

Immune-Mediated Encephalitis

In patients receiving Opdivo as a single agent, encephalitis occurred in 0.2% (3/1994). Fatal limbic encephalitis occurred in one patient after 7.2 months of exposure despite discontinuation of Opdivo and administration of corticosteroids. In the other two patients, encephalitis occurred post-allogeneic HSCT [see Warnings and Precautions].

Management

Evaluation of patients with neurologic symptoms may include, but not be limited to, consultation with a neurologist, brain MRI, and lumbar puncture.

Withhold Opdivo in patients with new-onset moderate to severe neurologic signs or symptoms and evaluate to rule out infectious or other causes of moderate to severe neurologic deterioration. If

other etiologies are ruled out, administer corticosteroids at a dose of 1 to 2 mg/kg/day prednisone equivalents for patients with immune-mediated encephalitis, followed by corticosteroid taper. Permanently discontinue Opdivo for immune-mediated encephalitis [see Dosage and Administration].

Other Immune-Mediated Adverse Reactions

Opdivo can cause other clinically significant and potentially fatal immune-mediated adverse reactions. Immune-mediated adverse reactions may occur after discontinuation of Opdivo therapy. For any suspected immune-mediated adverse reactions, first, exclude other causes and based on the severity of the adverse reaction, permanently discontinue or withhold Opdivo, administer high-dose corticosteroids, and if appropriate, initiate hormone-replacement therapy. Upon improvement to Grade 1 or less, initiate corticosteroid taper and continue to taper over at least 1 month. Consider restarting Opdivo after completion of corticosteroid taper based on the severity of the event [see Dosage and Administration].

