4.4 Duration of Study

A cycle is defined as q 4 weeks (28 days). Nivolumab and ONC201 will start on day 1 of each cycle (following an initial dose of ONC 201 on day -7). ONC201 will be given weekly day 1, and Nivolumab will be given q 2 weeks at a flat dose of 240mg IV over an approximate 30-minute infusion. See treatment section for details.

Dosing will continue until disease progression, unacceptable toxicity per patient or treating physician, or the patient discontinues for any other reason.

The maximum duration of treatment will be 12 months unless it is determined that a patient would derive benefit from continued therapy beyond 12 months, as determined by the investigator. Follow-up for all patients will be approximately 6 months.

The study is expected to be completed over an approximate 3.5-year period

When patients discontinue study treatment, they should return to the study site 30 days (+1 week) and 100 days (+1 week) after administration of the last treatment (Nivolumab or ONC201, whichever is last) to complete the safety assessment visit and procedures.

The study will be completed in approximately 3.5 years, taking into account approximately 2 years of enrollment, 12 months of treatment and approximately 6 months of follow-up, on average.

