6.6.6 Immune-mediated hepatitis and pancreatitis

Hepatic immune-related AEs are mostly clinically silent and manifested as transaminase or bilirubin laboratory abnormalities. Fatal hepatic failure has been reported in clinical trials of ipilimumab. **Serum transaminase, bilirubin and lipase levels must be evaluated before each protocol directed therapy infusion as early laboratory changes may be indicative of emerging immune-related hepatitis/ pancreatitis and elevations in liver function tests (LFTs) may develop in the absence of clinical symptoms.** Increase in LFT or total bilirubin should be evaluated to exclude other causes of hepatic injury, including infections, disease progression, or other medications, and monitored until resolution. Liver biopsies from patients who had immune-related hepatotoxicity have shown evidence of acute inflammation (neutrophils, lymphocytes, and macrophages).

Monitor levels of hepatic transaminases, bilirubin, and lipase and assess patients for signs and symptoms of hepatotoxicity/pancreatitis before each protocol directed therapy infusion. In patients with hepatotoxicity, rule out infectious or malignant causes and increase frequency of liver function test monitoring until resolution. Please see the Hepatic Adverse Management Guideline in Appendix D for further guidance.

The management of pancreatitis is given below.

Pancreatitis Amylase/Lipase	Management/Next Dose for Nivolumab
Grade 1	Continue protocol therapy and monitor. Asymptomatic lipase/amylase elevation, continue protocol therapy and monitor patient clinically.
Grade 2	For amylase/lipase elevations only, continue protocol therapy and monitor patient clinically. For radiographic findings consistent with pancreatitis, hold protocol therapy until resolved.

Pancreatitis Amylase/Lipase	Management/Next Dose for Nivolumab
Grade 3	Discontinue protocol therapy for development of Grade 3 pancreatitis or for new or worsening DM. Evaluate for co-existing hepatitis/cholecystitis. For amylase/lipase elevations only, continue protocol therapy and monitor patient clinically.
Grade 4	Discontinue protocol therapy for development of Grade 4 pancreatitis or for new or worsening DM. For amylase/lipase elevations only, continue protocol therapy and monitor patient clinically. Consider imaging if no improvement or worsening.

Pneumonitis

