Physical & HP (H&P due day 1, EOT and 30	X	Days 1, within 3 days	X within 3 days of	X within 3 days of dosing day 1	X	X	

day)		D15 (pre-nivo)	dosing day 1				
Vitals ^{1,8}	X	Days 1, within 3 days D15 (pre-nivo)	X within 3 days of dosing day 1 and day 15	X within 3 days of dosing day 1 and day 15	X	X	
Conmeds ¹⁷	X	Days 1, within 3 days D 15 (pre-nivo)	X within 3 days of dosing day 1 within 3 days of dosing day 1 and day 15	X within 3 days of dosing day 1 within 3 days of dosing day 1 and day 15	X	X	
PS	X	Days 1, within 3 days D 15 (pre-nivo)	X within 3 days of dosing day 1	X within 3 days of dosing day 1	X	X	
AE assessment	X	Days 1, within 3 days D 15 (pre-nivo)	X within 3 days of dosing day 1 within 3 days of dosing day 1 and 15	X within 3 days of dosing day 1 within 3 days of dosing day 1 and 15	X	X	
DLT assessment	X	Days 1, within 3 days D 15 (pre-nivo)	X (DLT assessment completed pre-cycle 2 day 1)				
EKG ¹⁶		as clinically indicated	as clinically indicated	as clinically indicated	as clinically indicated		
CT C/A/P ³			At week 8 (+1 week) ³	Every 8 weeks (+1 week) ³	X unless one was completed in prior 4 weeks		X ³
Brain MRI for patients with brain mets 3			X	X	X unless one was complet		X ³

					ed in prior 4 weeks		
Bone scan or bone X-Ray for patients with bone metastases ³		X	X	X unless one was completed in prior 4 weeks		X ³	
CBC w/diff, plts ^{4,8}		⁸ Weekly within 24 hours of dosing each day	X within 3 days of dosing day 1 and day 15	X within 3 days of dosing day 1 and day 15	X		
Serum chemistry ^{5,8}		⁸ Weekly within 24 hours of dosing each day	X within 3 days of dosing day 1 and day 15	X within 3 days of dosing day 1 and day 15	X		
TSH and coagulation ^{6,8}		⁸ X D1 only	X within 3 days day 1 only	X within 3 days day 1 only	X		
HCG ^{7,8}		X ^{7,8}	X	X			
PK plasma ⁹ (Phase IB patients only)	X ⁹	X ⁹ See schedule for all requirements D1,2,3,7	X ⁹ See schedule for all requirements D1,2,3,7	X ⁹			
Blood sample for PD ¹⁰	X ¹⁰	X ¹⁰ See schedule for all requirements D1,2,3,7	X ¹⁰ See schedule for all requirements D1,2,3,7	X ¹⁰			
cfDNA ¹¹		X prior to D15 dosing	X	X			
Tumor biopsy ¹³⁺¹²			Week 8 (+/- 7 days)		Biopsy at progression if patient has not progressed ¹³		

Survival and disease status							X ¹⁵
-----------------------------	--	--	--	--	--	--	-----------------

*ONC201 is to be taken by patient in front of research staff day -7, day 1, day 8, day 15, day 22 in cycle 1.

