¹¹ cfDNA: blood to be collected at baseline (pre-dosing ONC201, prior to day -7 cycle 1) and prior to ONC201 and Nivolumab (twice a cycle with pre-Nivolumab labs) cycles 1-6. Cycles 7-on: CfDNA will be collected pre-dosing each cycle day 1 only. CfDNA will not be collected once patient progresses. If patient remains on study post 12 cycles, cfDNA will only be drawn pre-dosing day 1 of each cycle: **Collect CfDNA whole blood sample in 1 K2EDTA tube. Post collection, invert sample 8-10 times and let site at room temperature. See section 11.1.3.**

¹² Subjects providing informed consent will have tumor biopsy performed pre-treatment, at approximately 8 weeks when the first tumor imaging assessment is performed, and at the time of progression. For those patients whose disease is progressing at the first post-treatment imaging assessment at 8 weeks they will only have 2 biopsies.

¹³ Tissue from a biopsy (at least 3-6 cores in 10% neutral buffered formalin) will be obtained by radiologic guidance and sent to the laboratory of [name]. Only 2 biopsies will be required for patients who progress at the end of cycle 2.

¹⁴ Off-study evaluation to occur post completion of entire cycle. Follow-up visits or other contact are required in order to identify SAEs during the first 100 days (+1 weeks) following the end of study treatment (Nivolumab, or ONC201), respectively. There will be a safety visit at 30 days (+1 week) and 100 days (+1 week) time points. SAEs need to be reported after 100 days if the SAE is thought to be related to study treatment. 30-day and 100-day safety evaluation time points required for all patients who receive at least one dose of drug on BrUOG 379, unless they withdraw consent.

¹⁵ Survival and disease status will be collected for all patients who receive at least one dose of ONC201 once they come treatment (unless they withdraw consent), approximately every 3 months for (+/- 1 month) 6 months

¹⁶ EKG registration and as clinically indicated. Any findings from EKGs collected after initiation of study treatment will be captured as AEs if, in the opinion of the investigator, there has been a clinically significant change from baseline.

¹⁷ Medications used by the patient and therapeutic procedures completed by the patient will be recorded in the CRF from screening through 100 days after the last dose of study drug or the start of subsequent antineoplastic therapy, whichever occurs first.

9 Criteria for Taking a Participant Off Protocol Therapy

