12.5 BRUOG ADVERSE EVENT REPORTING REQUIREMENTS

Investigators are required by Federal Regulation to report adverse drug reactions. Questions regarding drugs as used in this study should be directed to the Brown University Oncology Research Group (BrUOG) Central Office, [contact] [contact], which will in turn notify the Principal Investigator.

All adverse events and special reporting situations, whether serious or non-serious, related or unrelated, will be reported from the time a signed and dated ICF is obtained until 100 days (+1 week) after the last treatment (Nivolumab or ONC201, whichever is last), or until the subject withdraws consent from study participation (declines participation) or at the time patient becomes a screen failure, whichever occurs first. There will be a safety visit at 30 days (+1 week) and 100 days (+1 week) time points.

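### No laboratory test is scheduled after the off-study visit, so silent immune toxicity in most of the 100-day adverse-event window is found only if someone orders a test

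*Combined protocol and SAP*

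**What the plan says.** **Collection window.** Section 12.5 states that all adverse events, of any seriousness or attribution, "will be reported from the time a signed and dated ICF is obtained until 100 days (+1 week) after the last treatment" of either drug. Section 12.3 includes abnormal laboratory findings in the definition of an adverse event.

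**Visits in the window.** Section 4.4 brings patients back to the site at 30 and 100 days "to complete the safety assessment visit and procedures". Footnote 14 in section 8 repeats this: "There will be a safety visit at 30 days (+1 week) and 100 days (+1 week) time points". It makes both time points mandatory for anyone who received a dose, unless consent is withdrawn.

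**What is done there.** In the section 8 during-treatment table, the 30/100-day column is marked for physical exam, vitals, concomitant medication, performance status and adverse-event assessment. It is blank for three rows:

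- blood count and serum chemistry, whose cycle 1 cell reads "Weekly within 24 hours of dosing each day" (this identifies the rows; the evidence is the blank cell further right);
- TSH and coagulation, marked in treatment cycles as "X within 3 days day 1 only".

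The last mark in each row is the off-study visit, and no footnote adds a later test.

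**What the protocol says about the toxicity.** Section 6.6.6: "Hepatic immune-related AEs are mostly clinically silent and manifested as transaminase or bilirubin laboratory abnormalities". Section 2.2.3: "Immune-mediated adverse reactions may occur after discontinuation of Opdivo therapy".

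**The concern.** The sponsor chose a long window because immune toxicity can appear late, and it requires two visits inside that window. The tools at those visits are history and examination. CTCAE grades for transaminases, bilirubin, creatinine, amylase and blood counts need a measured value, and by the protocol's own account the hepatic events are mostly silent.

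Safety by CTCAE v5.0 is a secondary objective in both phases. If late laboratory events are sought only when a clinician has a reason to test, the reported frequency depends on local testing habits and on how ill the patient is, and it errs low. With 34 patients at the recommended phase II dose, one missed event moves an observed rate by 1/34, or 2.9 percentage points. A patient with silent toxicity could also attend a study visit without its being found.

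**Working it through.** The plan gives no figure to reproduce. The check has two parts.

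**1. How much of the window has no scheduled panel?**

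Inputs: 28-day cycles (section 4.4); ONC201 weekly, and nivolumab on days 1 and 15 (section 4.2); off-study visit after completion of the whole cycle, +7 days (section 8 table header and footnote 14). Assumption: the last cycle runs its full 28 days.

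The panel falls between (29 − D) and (29 − D + 7) days after the last dose, where D is the cycle day of that dose. The untested remainder is 100 minus these limits.

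| Last dose on cycle day | Off-study panel, days after last dose | Untested days to day 100 | To day 107 (+1 week) |
|---|---|---|---|
| 1 | 28–35 | 65–72 | 72–79 |
| 8 | 21–28 | 72–79 | 79–86 |
| 15 | 14–21 | 79–86 | 86–93 |
| 22 | 7–14 | 86–93 | 93–100 |

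Every patient who has the off-study evaluation therefore has one scheduled panel inside the window. The gap is the 65 to 93 days after it.

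**2. How many events could fall in that gap?**

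Inputs from section 2.2.3 (single-agent nivolumab; rate, median onset):

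- hepatitis 1.8%, 3.3 months
- hypothyroidism 9%, 2.9 months
- hyperthyroidism 2.7%, 1.5 months
- nephritis and renal dysfunction 1.2%, 4.6 months
- diabetes 0.9%, 4.4 months

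Expected events: 34 × (1.8 + 9 + 2.7 + 1.2 + 0.9)% = 34 × 15.6% = 5.3.

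Assumptions, not in the documents: onset is exponential with median m; time to end of treatment is exponential and independent, with median M. I take M = 3 months (50% progression-free at 3 months, the null in section 16.4) and M = 6 months (its alternative). Then

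P(onset between d₁ and d₂ after stopping) = [m/(m + M)] × (e^(−a·d₁) − e^(−a·d₂)), with a = ln 2/m.

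Example: hypothyroidism, M = 3, panel at day 14 (0.46 months), window end at day 100 (3.285 months). Here m/(m + M) = 2.9/5.9 = 0.492 and a = 0.239 per month. The result is 0.492 × (0.896 − 0.456) = 0.216.

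Range over the five toxicities:

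| Share of onsets | M = 3 months | M = 6 months |
|---|---|---|
| Any time after last dose | 33–61% | 20–43% |
| Day 0 to day 100 | 24–27% | 16–18% |
| Panel at day 7, to day 100 | 22–24% | 14–16% |
| Panel at day 14, to day 100 | 20–22% | 12–14% |
| Panel at day 35, to day 100 | 12–15% | 7–10% |

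With the off-study panel credited, the share in the untested stretch is 12–24% for M = 3 and 7–16% for M = 6. Applied to 5.3 events, the extremes are 0.07 × 5.3 = 0.4 and 0.24 × 5.3 = 1.3.

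**The case against.** A reader might infer from the blank cells that laboratory toxicity cannot be scored at all after the last dose, for any patient. The documents do not support that. The off-study panel is itself after the last dose and inside the window. Section 6.6.4 allows further endocrine evaluation when clinically indicated, section 6.6.6 follows raised liver tests to resolution, and any abnormal result counts as an adverse event under section 12.3. A patient who stops nivolumab but continues ONC201 under section 6.2 keeps the on-treatment laboratory schedule. Nor do the documents say that an untested value is recorded as no event; they give no rule on this.

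The size can also be challenged, fairly. The section 2.2.3 rates cover symptomatic events too, which the adverse-event assessment should catch: the diabetes figure includes two ketoacidosis cases, and section 6.6 grades thyroid events by symptoms. Hypothyroidism supplies more than half of the 5.3, which counts events and not patients. Risk may fall after stopping. All of this makes the calculation an upper estimate.

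Finally, no stated decision turns on the gap. The dose-limiting-toxicity window closes before cycle 2 dosing, and section 16 defines no estimate or test on the 100-day window.

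What remains is that, after the off-study panel, detection of a silent event depends on an unscheduled test, in a window the protocol set for late toxicity and at visits the patient already attends.

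**Conclusion.** The point holds as incomplete and uneven ascertainment. For roughly the last 65–93 days of the 100-day window, if the last cycle is completed, no laboratory test is scheduled, and asymptomatic laboratory-detected events are found only by chance or clinical prompting. The likely direction is under-counting.

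The size is modest: at most about 0.4–1.3 of 5.3 expected events in 34 patients. That rests on exponential onset and treatment times, median treatment of 3 or 6 months, and single-agent rates, since the combination's rates are unknown. The number of silent events actually missed would be smaller and cannot be estimated from the documents. Phase Ib dose decisions and the primary efficacy analysis do not change. The change is worth making because it is cheap and gives every patient the same ascertainment.

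**What to change.** In the section 8 during-treatment table, mark blood count, serum chemistry (the footnote 5 panel) and TSH in the 30-day/100-day safety-visit column. No new reporting rule is needed, because sections 12.3 and 12.5 already make abnormal results in that window reportable.

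The cost is two routine blood draws per patient at visits already required, plus a table amendment; no extra visit is added. Two limits should be accepted. Day-100 values may be harder to attribute in patients who have started another anticancer therapy, particularly as footnote 17 ends concomitant-medication recording at that point. And footnote 5 lists amylase but not lipase, whereas section 6.6.6 requires lipase before each infusion; that mismatch should be reconciled when the table is amended.
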